#### 11.1.4 Life-threatening (21 CFR 312.32(a))

An adverse event or suspected adverse reaction is considered "life-threatening" if, in the view of either the investigator or sponsor, its occurrence places the patient or subject at immediate risk of death. It does not include an adverse event or suspected adverse reaction that, had it occurred in a more severe form, might have caused death.

The SI will fulfill the reporting responsibilities to FDA on behalf of Nationwide Children's Hospital using the web-based Adverse Event reporting system (GeMCRIS).

# 11.2 Relationship to Study Drug

Association or relatedness to the study agent, study procedures and the subject's pre-existing disease will be graded as follows:

- 1. Definitely related
- 2. Probably related
- **3.** Possibly related
- 4. Unlikely related
- **5.** Unrelated

If the relationship between the AE/SAE and the investigational product is determined to be "possible" or "probable", the event will be considered to be related to the investigational product for the purposes of expedited regulatory reporting.

# 11.3 Time Period and Frequency for Event Assessment and Follow-Up

# 11.3.1 Obligations of the Investigator

The Sponsor Investigator will submit an IND safety report to the FDA on any serious adverse event that is both unexpected and associated with the use of the gene transfer product (i.e., there is reasonable possibility that the event may have been caused by the use of the product; the investigator will not await definitive proof of association before reporting such events); as well as a written report on any finding from tests in laboratory animals that suggests a significant risk for human research participants including reports of mutagenicity, teratogenicity, or carcinogenicity. The report will be clearly labeled as a "Safety Report" and will be submitted to the FDA and to the local Institutional Review Board within the timeframes set forth in Section 11.3.2.

The Sponsor Investigator will adhere to any other serious adverse event reporting requirements in accordance with federal regulations, state laws, and the local institutional policies and procedures, as applicable.

The Sponsor Investigator will be responsible for ensuring that the reporting requirements are fulfilled and will be held accountable for any reporting lapses.

# 11.3.2 Safety Reporting

The investigator or his designee will report all serious and unexpected adverse events to the IRB, CBER/FDA and DSMB according to regulatory requirements described as follows:

- **IRB**: All Serious Adverse Events (SAEs) and Dose Limiting Toxicities (DLTs), regardless of expectedness, relatedness, or if they meet the definition for unexpected problems in the clinical trial will be reported to the **IRB** as soon as possible, but not later than **15 calendar days** after the sponsor's initial receipt of the information.
- **DSMB**: All Serious Adverse Events (SAEs) and Dose Limiting Toxicities (DLTs) that are lifethreatening will be reported to the **DSMB** within 48 hours of notification, regardless of expectedness, relatedness, or if they meet the definition for unexpected problems to the clinical trial.
- **FDA:** Any serious adverse event that is fatal or life-threatening, that is unexpected, and associated with the use of the gene transfer product will be reported by the study investigator to the **FDA** as soon as possible, but not later than **7 calendar days** after the sponsor's initial receipt of the information.

Serious adverse events that are unexpected and associated with the use of the gene transfer product, but are not fatal or life-threatening, will be reported to the **FDA** as soon as possible, but not later than 15 calendar days after the sponsor's initial receipt of the information.

Changes in this schedule will be permitted only where, under the **FDA IND** regulations [21 CFR 312(c) (3)], changes in this reporting schedule have been approved by the FDA and are reflected in the protocol.

If, after further evaluation, an adverse event initially considered not to be associated with the use of the gene transfer product is subsequently determined to be associated, then the event will be

reported to the **FDA** as soon as possible, but in no case later than **15 calendar** days after the determination is made.

Relevant additional clinical and laboratory data will become available following the initial serious adverse event report. Relevant follow-up information to an IND safety report will be submitted concurrently to the **FDA/IRB and the DSMB** as soon as the information is available and will be identified as such, i.e., "Follow-up IND Safety Report." If a serious adverse event occurs after the end of a clinical trial and is determined to be associated with the use of the gene transfer product, that event will be reported concurrently to the **FDA** within 15 calendar days of the determination.

Any finding from tests in laboratory animals that suggests a significant risk for human research participants including reports of mutagenicity, teratogenicity, or carcinogenicity will be reported to **FDA** and the **DSMB** as soon as possible, but not later than 15 calendar days after the sponsor's initial receipt of the information.

Should a serious adverse event deemed possibly, probably or definitely related to the study agent occur during administration, the study agent will be discontinued, appropriate treatment will be given under medical supervision and the subject will be examined as frequently as necessary thereafter until symptoms cease or stabilize.

## 11.3.3 Safety Reporting: Content and Format

The serious adverse event report will include, but need not be limited to: (1) the date of the event; (2) designation of the report as an initial report or a follow-up report, identification of all safety reports previously filed for the clinical protocol concerning a similar adverse event, and an analysis of the significance of the adverse event in light of previous similar reports; (3) clinical site; (4) the Sponsor Investigator; (5) FDA's Investigational New Drug (IND) application number; (6) vector type, e.g., adeno-associated virus; (7) vector subtype, if relevant; (8) gene delivery method, e.g., *in vivo* transduction; (9) route of administration, e.g., intramuscular; (10) dosing schedule; (11) a complete description of the event; (12) relevant clinical observations; (13) relevant clinical history; (14) relevant tests that were or are planned to be conducted; (15) date of any treatment of the event; and (16) the suspected cause of the event. These items will be reported through an FDA safety report by using the recommended Adverse Event Reporting Template available on NIH's web site at:

http://osp.od.nih.gov/sites/default/files/resources/Adverse Event Template .docx

# 11.3.4 Adverse Event Reporting from Primary Care Physician

Close communication will be established with the primary care physician of all study participants and will be maintained throughout the study. The important hallmarks of the study along with the proposed reporting plan will be explained. We will request that the primary care physician provide information regarding every routine visit and any intercurrent event taking place during the two years following gene transfer. Laboratory reports, hospitalizations, clinical notes and any other relevant medical records will be requested at the time of their occurrence. If non-routine visits are reported to us by the primary care physician, the study investigator will initiate an investigation to determine the possibility of an adverse event related to the gene transfer and will adhere to the adverse event reporting requirements in accordance with federal regulations, state laws, and the local institutional policies and procedures, as applicable.

During the consent process, the study investigator will emphasize the importance of subject communication with our study team. Any routine or non-routine doctor's visits or medical care

received during the two years following gene transfer should be reported to the study team. The study doctor will explain to the participant that copies of any relevant medical records of those visits will be requested from their medical care provider.

## 11.3.5 Follow-up of Adverse Events

All adverse events will be followed until resolution or stabilization.

# 11.4 Dose limiting toxicity (DLT)

Dose limiting toxicity is defined as any adverse event that is possibly, probably, or definitely related to the study agent, and is unexpected. This would include any grade 3 event, according to the Common Terminology Criteria for Adverse Events (CTCAE) version 5.0; these classifications are outlined in **Table 10**.

Note: Elevations in transaminases and transient alterations in WBCs, as outlined in Section 12.4.2, above, are expected, and will not be considered as dose limiting when within the ranges noted therein.

Table 10: Adverse Event Classification

1	Mild adverse event; did not require treatment
2	Moderate adverse event; resolved with treatment
3	Severe adverse event; inability to carry on normal activities; required professional
	medical attention
4	Life-threatening or permanently disabling adverse event
5	Fatal adverse event

Study enrollment will be halted by the investigators when any subject experiences two or more **Grade 3**, **or higher** adverse event toxicity that are unexpected and **possibly**, **probably**, **or definitely related** to the study drug. The event will then be reviewed by the Data Safety Monitoring Board (DSMB) before making a determination to continue enrollment as described in Section 0.

Laboratory tests with values within the clinically significant range will be repeated during the same visit whenever possible (refer to CTCAE v5.0 for a complete list of clinically significant range values). If the test result returns after the subject leaves the clinic, they will be immediately contacted. For local residents they will be asked to return to the outpatient clinic for a repeat test. For non-local residents, arrangements will be made to have the blood test redrawn in a laboratory close to home or by their primary care physician. To avoid any confusion for the primary care physician, they will be informed (with permission from the subject) of their participation in the study at the time of gene transfer. If the AE requires treatment, this will be carried out by the primary care physician or a doctor of choice selected by the subject. We will obtain copies of repeat laboratory tests and any relevant medical records that will be added to the subject's research chart.

The SI will fulfill the reporting responsibilities under 21 CFR 312.32(c), to notify FDA in an IND safety report of potentially serious risks, as soon as possible, but no later than 15 calendar days after the investigator receives the safety information and determines that the information

qualifies for reporting. The investigator will confer with the DSMB and FDA before continuing to enroll.

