#### 5 OBJECTIVES AND PURPOSE

## **5.1 Primary Outcome**

Safety is the primary outcome for this clinical gene transfer trial. Stopping criteria are based on development of unacceptable toxicity defined as the occurrence of two or more unexpected Grade III or higher treatment-related toxicities.

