## 11.1 Adverse and Serious Adverse Event

## 11.1.1 Definition of an Adverse Event

As stated above this protocol will follow the final regulations issued by the Food and Drug Administration addressing the safety reporting requirements for investigational new drug applications (INDs) found in 21 CFR part 312 and for bioavailability and bioequivalence studies found in 21 CFR part 320. "Safety Reporting Requirements for INDs and BA/BE Studies".

 $\frac{http://www.fda.gov/downloads/Drugs/GuidanceComplianceRegulatoryInformation/Guidances/UCM227351.pdf}{CM227351.pdf}$ 

**Adverse Event (AE)**: Adverse event means any untoward medical occurrence associated with the use of a drug in humans, whether or not considered drug related.

Adverse events will be graded by the investigator accordingly (as indicated in Section 11.4):

- 1 = mild
- 2 = moderate
- 3 = severe
- 4 =life threatening or debilitating
- 5 = fatal

Association or relatedness to the study agent will be graded as follows:

- 5 = unrelated
- 4 = unlikely
- 3 = possibly
- 2 = probably
- 1 = definitely related.

**Adverse reaction:** An adverse reaction means any adverse event caused by a drug. Adverse reactions are a subset of all suspected adverse reactions for which there is reason to conclude that the drug caused the event.

Suspected adverse reaction (21 CFR 312.32(a)) Suspected adverse reaction (SAR) means any adverse event for which there is a reasonable possibility that the drug caused the adverse event. For the purposes of IND safety reporting, 'reasonable possibility' means there is evidence to suggest a causal relationship between the drug and the adverse event. A suspected adverse reaction implies a lesser degree of certainty about causality than adverse reaction, which means any adverse event caused by a drug.

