#### 11.5 Discontinuation Rules

An independent Data Safety Monitoring Board (DSMB) will be established. Safety data will be monitored on a continual basis throughout the trial. The DSMB can recommend early termination of the trial for reasons of safety. Study enrollment will be halted by the investigators when any subject experiences two or more Grade 3, or higher adverse events that are **unexpected** and **possibly, probably, or definitely related** to the study drug. This will include any subject death, important clinical laboratory finding, or any severe local complication in the injected area related to administration of the study agent. If after review by the DSMB, the decision is made to continue, the study will proceed according to Section 6.4 of this protocol.

The investigators will confer with the DSMB on all Grade 3 or higher adverse events that are possibly, probably, or definitely related to the study agent before continuing enrollment.

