# 12.1.3 **DSMB** Reporting and Meetings

Reports describing the status of the study will be prepared by the Sponsor Investigator's staff and sent to the DSMB prior to a meeting, or at the DSMB's request.

A meeting (either by teleconference or webcast) with the DSMB will be scheduled prior to study initiation, after the Day 30 visit of the first subject and then approximately every 6 months, or at the DSMB's request. Reports will be submitted prior to a scheduled meeting for review by the DSMB.

Reports will include the following:

- A brief narrative of the study status, including the target enrollment, current and projected time to completing enrollment. Any significant events and/or difficulties should be briefly described in this narrative.
- A brief narrative for each participant describing gender, age, race and ethnicity and other relevant demographic characteristics. The narrative for each participant should briefly describe his/her study status (i.e., dose level, visit number, adverse event information);
- A timeline outlining the study progress relative to visit number for each participant, as well as time points for each SAE/Dose Limiting Toxicity. A total for Adverse Events (AEs) for each participant should be included.
- A summary of AEs by severity levels;
- A listing of AE details grouped by participant;
- A listing of SAE details grouped by participant;
- A listing of deaths
- · A summary of clinically significant laboratory test results

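### The DSMB consultation in Section 11.5 depends on the relatedness call, so after subject 1's Day 30 review a Grade 3 event called unrelated is not clearly required to reach the board before the next infusion

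*Combined protocol and SAP*

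**What the plan says.** **Halt.** Section 11.4: "Study enrollment will be halted by the investigators when any subject experiences two or more" events of Grade 3 or higher "adverse event toxicity that are unexpected and" at least possibly related to the study drug. Section 5.1 gives the criterion as "the occurrence of two or more unexpected Grade III or higher treatment-related toxicities". Sections 6.5 and 11.5 repeat the rule and add: "This will include any subject death, important clinical laboratory finding, or any severe local complication in the injected area". It is unclear whether the relatedness qualifier that ends that sentence applies to all three items or only to the last.

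**Consultation.** The last sentence of 11.5 reads: "The investigators will confer with the DSMB on all Grade 3 or higher adverse events that are possibly, probably, or definitely related". This has to happen before enrollment goes on. One event is enough and it need not be unexpected, but it must already be called at least possibly related.

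**Who decides.** On severity, 11.1.1 says: "Adverse events will be graded by the investigator accordingly". For relatedness, 11.1.1 and 11.2 give a five-point scale in the passive voice and name no assessor.

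**Routes to the DSMB that do not depend on attribution.**
- Section 6.1 leaves at least six weeks between subjects 1 and 2, so that the DSMB can review five time points up to Day 30. It requires no 30-day time point between later subjects.
- Section 12.1.3 schedules meetings before initiation, "after the Day 30 visit of the first subject and then approximately every 6 months", or when the board asks. The reports list all adverse events by participant.
- Section 11.3.2 sends life-threatening events to the DSMB within 48 hours regardless of relatedness. Section 11.4.1 takes events attributed to disease progression out of the expedited rules.

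**The concern.** Safety is the primary outcome, and the rules that bring an event to the DSMB before another boy is infused are its main protection. The halt and the 11.5 consultation both pass through one judgement, relatedness, that nobody independent is described as checking. The study is open-label and led by a sponsor-investigator. These boys have a progressive disease, anaesthesia, repeated biopsies and raised corticosteroid doses, so another cause will often be plausible for a severe event.

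If a related Grade 3 event is called unlikely or unrelated, it does not count towards the halt and does not trigger the consultation. The next infusion could then go ahead before the DSMB has seen it.

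**Working it through.** The plan states no operating characteristic for the halt or the consultation, so there is no figure to reproduce. The check traces one event through the rules, then works out the timing and a simple probability.

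**1. Route of a Grade 3 event that is not life-threatening and is called unlikely or unrelated**

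| Route | Reached? |
|---|---|
| Numerical halt (5.1, 6.5, 11.4, 11.5) | No: relatedness required |
| DSMB consultation (11.5, last sentence) | No: relatedness required |
| DSMB report in 48 hours (11.3.2) | Unclear, see below |
| IRB report in 15 calendar days (11.3.2) | Yes, unless attributed to disease progression (11.4.1) |
| DSMB review before subject 2 (6.1, 12.1.3) | Yes, for subject 1 through Day 30 |
| Periodic DSMB meeting (12.1.3) | Yes, but about 6 months apart |

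The DSMB item in 11.3.2 can be read two ways. If the life-threatening qualifier covers both SAEs and DLTs, this event is outside it. If it covers only DLTs, the event is inside it, because 11.1.3 makes every category 3 event an SAE. On either reading an event attributed to disease progression drops out, and the item requires a report, not a wait before the next infusion.

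The closing paragraph of 11.4 also has the investigator confer with the DSMB and FDA before enrolling further. It does so in the context of an IND safety report, which under 11.3.1 is itself limited to associated events.

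**2. Timing**

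- Earliest dosing of subject 2: 6 × 7 = Day 42 of subject 1.
- Latest Day 30 visit: 30 + 3 = Day 33 (window in 9.1.3.3). This leaves at least 42 − 33 = 9 days for the DSMB review.
- Days 31 to 42 fall outside the five named time points: 42 − 30 = 12 days at the minimum interval, and more if subject 2 is dosed later.
- With up to three subjects (6.3) there are at most two transitions. For subject 2 to subject 3, no interval and no DSMB review are stated.

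**3. Size**

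Let s be the probability that a truly related Grade 3 event is called at least possibly related. The documents give no value, so s is assumed.

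- One event: consultation lost with probability 1 − s. The numerical halt is not reached at any s, because it needs two events.
- Two independent events in one boy: consultation lost for both with probability (1 − s)².

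| s | One event: 1 − s | Two events: (1 − s)² |
|---|---|---|
| 0.9 | 10% | 1% |
| 0.8 | 20% | 4% |
| 0.7 | 30% | 9% |

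If the same assessor's errors go together, the two-event figure rises towards 1 − s. With the relatedness condition removed, the consultation would be required for every event graded 3 or higher, whatever s is.

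**The case against.** The case for leaving the text alone has real content:

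- The first transition is covered. Subject 1's events through Day 30 reach the DSMB before subject 2, in listings not filtered by attribution. With one to three subjects, there may be only one further transition, or none.
- A call of possibly related already counts, so only unlikely or unrelated calls escape.
- Life-threatening events have a 48-hour route, the IRB receives all SAEs within 15 days, safety data are monitored continually, and the board can ask for a meeting.

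All of this stands and narrows the point, but it does not close it. The IRB deadline is not tied to the next infusion, the board cannot readily ask about an event it has not been shown, and the 48-hour rule is ambiguous for Grade 3 events.

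A reader might infer that any miscalled Grade 3 event can stay hidden from the board for six months. Section 6.1, the second reading of 11.3.2, and meetings at the board's request do not support that.

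A reader might also take 1 − s² (19%, 36% and 51% at s = 0.9, 0.8 and 0.7) as the failure rate. That is the chance of missing the numerical halt after two related events. It ignores the 11.5 consultation, which takes a single related event to the DSMB before enrollment continues.

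Finally, the documents do not say that the investigators assign relatedness. It is a fair inference, since they grade severity (11.1.1), look into reported non-routine visits (11.3.4) and operate the halt, but it remains an inference.

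**Conclusion.** The point holds in a limited form. The halt and the pre-enrollment consultation both depend on an attribution that no independent party is described as checking. The gap concerns Grade 3 events that are not life-threatening and are called unlikely or unrelated, in two periods: subject 1 after Day 30, and between subjects 2 and 3. In those periods no rule clearly puts such an event before the DSMB ahead of the next infusion.

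The consultation is lost for 10% to 30% of single related events, and for both of two independent events 1% to 9% of the time, at s from 0.9 to 0.7. These figures rest on an assumed s, and the second also on independent calls. They illustrate scale and do not estimate this team's accuracy.

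The plan already reports SAEs to the IRB, and life-threatening ones to the DSMB, without regard to relatedness. Extending that principle to the consultation is a cheap improvement and should be made. The documents do not support the further step of making the DSMB the adjudicator of the halt count: Section 12.1 gives it an advisory role, and changing that is a separate and debatable choice.

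**What to change.** - In the last sentence of 11.5, delete the relatedness condition, so that the investigators confer with the DSMB on every Grade 3 or higher event, whatever its attribution, before the next infusion.
- Align 6.5 and 11.4 with that sentence.
- In 11.3.2, state whether the life-threatening qualifier in the DSMB item covers SAEs or only DLTs, and reconcile the result with the disease-progression exception in 11.4.1.
- Leave the halt count unchanged.

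The cost is protocol wording and a few extra reviews by an existing board for at most three boys. The downside is an occasional short wait for an event that proves unrelated. That could matter for a sibling awaiting infusion, since 6.1 omits the later interval out of concern that shedding could induce excluding antibodies in the second child.
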